3.2 Secondary Endpoints

1. Surgical Site Occurrence (defined as surgical site infection (see Appendix 2 for definitions), seroma, hematoma, wound dehiscence, skin necrosis, mesh infection and fistulas requiring intervention) > 45-days post-implantation
2. Hernia Recurrence Rate will be assessed by physical examination at each study visit through 24-months. A recurrent hernia will be defined as any hernia identified or confirmed by the investigator, during any study follow-up visit, within 5 cm of the hernia repaired in the study procedure.
3. Surgical Pain Scale - Visual Analog Scale (VAS)
4. Device related adverse event incidence
5. Rate of reoperation due to the index hernia repair
6. Quality of life assessments (Carolinas Comfort Scale® and SF-12®)
7. Surgical procedure time as measured from incision to closure (skin to skin)
8. Length of stay

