7.3 Data Analysis

The Intent-to-treat (ITT) population consists of all enrolled subjects who have signed the Informed Consent Form. The modified ITT (mITT) population is defined as those subjects in the ITT population in whom Phasix Mesh has been implanted. A Per-Protocol (PP) population may be created if there are subjects who have any major protocol deviations. The PP population will consist of any subjects in the mITT population who do not have any major protocol deviation. The protocol deviations that are considered to have a “major” grade will be defined a priori in the analysis plan. All analyses will be primarily based on the mITT population. Primary analyses may be performed for PP population as well.

Demographics and baseline characteristics will be summarized using the ITT population. Summary statistics for categorical variables will include frequency counts and percentages and for continuous variables mean, standard deviation, minimum, median and maximum.

The primary endpoint of SSO within 45 days post-implantation will be reported by visit along with the 95% confidence intervals based on the mITT population. The calculation of rates at each time point will be based on available data at the time point. Missing data will not be imputed. Additionally, a Kaplan-Meier survival analysis will be performed.

The secondary endpoints of SSO > 45 days post-implantation, hernia recurrence rate, pain – VAS, device related adverse event incidence, rate of reoperation due to the index hernia repair, Quality of life assessments (Surgical Pain Scale -VAS, Carolinas Comfort Scale® and SF-12®), surgical procedure time as measured from incision to closure (skin to skin) and length of stay will be summarized based on the mITT population with mean, standard deviation, minimum, median and maximum presented by visit. Other secondary endpoints will be summarized as appropriate.

Subjects who do not have Phasix™ ST implanted will have their AEs summarized separately and their outcome data will not be collected or analyzed.

Exploratory analyses on subpopulations may be performed. Interim analyses may be conducted during the study for data review purpose.

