#### 2.2.2 Secondary Endpoints

1. Surgical Site Occurrence (SSO) (defined as one of the following complications requiring intervention: surgical site infection, seroma, hematoma, wound dehiscence, skin necrosis, mesh infection and fistulas) > 45-days post-implantation follow-up assessment
2. Hernia Recurrence Rate will be assessed by physical examination at each study visit through 24-months. A recurrent hernia will be defined as any hernia identified or confirmed by the investigator, during any study follow-up visit, within 5 cm of the hernia repaired in the study procedure.
3. Surgical Pain Scale - Visual Analog Scale (VAS)
4. Device-related adverse event incidence
5. Rate of reoperation due to the index hernia repair
6. Quality of life assessments (Carolinas Comfort Scale® and SF-12v2®)
7. Surgical procedure time as measured from incision to closure (skin to skin)

8. Length of stay in hospital (day of index surgery until day of discharge, LOS)

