#### **5.2 Hernia Recurrence Rate**

The proportion of subjects with Hernia Recurrence and confidence intervals of the rate from exact binomial test will be reported by each visit window, including both cumulative (overall rate) and disjointed intervals.

The start date of the hernia recurrence minus the implantation date will determine the interval of hernia recurrence.

Only evaluable subjects will be included in the denominator and evaluable subjects are defined as following: 1) For cumulative intervals, any subjects with Phasix™ ST Mesh implanted will be included in this analysis. 2) For disjointed intervals, if a subject discontinues before the intervals begins then that subject is considered as not evaluable for that particular interval analysis. Note: if subject did not come for a scheduled clinical visit (of the report period), but it was known that the subject was in the study and did not report hernia recurrence during the respective time interval, then the subject will be considered as free from the recurrence.

Hernia Recurrence in the same location as index procedure is identified by physical exam or any other means from post-operative CRF pages at scheduled or unscheduled visits. Analysis is based on mITT population (all subjects implanted with Phasix™ ST Mesh).

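### SAP 5.2 counts an enrolled subject who missed the visit and reported nothing as recurrence-free, so interval recurrence rates are too low whenever such a subject has a recurrence that is not later found and dated back

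*SAP*

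**What the plan says.** Protocol 3.2 sets the method of assessment: "Hernia Recurrence Rate will be assessed by physical examination at each study visit through 24-months". It then defines the event: "A recurrent hernia will be defined as any hernia identified or confirmed by the investigator, during any study follow-up visit, within 5 cm", measured from the repaired hernia. SAP 2.2.2 repeats that definition ("any hernia identified or confirmed by the investigator, during any study follow-up visit").

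SAP 5.2 reports the recurrence proportion with exact binomial intervals by visit window, both cumulatively and for disjoint intervals. A recurrence is placed in an interval by its start date minus the implantation date. The denominators are:

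- **Cumulative:** "For cumulative intervals, any subjects with Phasix™ ST Mesh implanted will be included in this analysis".
- **Disjoint:** "if a subject discontinues before the intervals begins then that subject is considered as not evaluable for that particular interval analysis".
- **Missed visit (the Note):** this covers the case "if subject did not come for a scheduled clinical visit (of the report period), but it was known that the subject was in the study". It goes on that where such a subject "did not report hernia recurrence during the respective time interval, then the subject will be considered as free from the recurrence".

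SAP 5.2 also accepts recurrences found by means other than physical examination, provided that they come from the CRF pages of scheduled or unscheduled visits.

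**The concern.** The endpoint needs an investigator's finding. The Note lets the absence of a report from the subject stand in for it. The only condition is that the subject was known to be in the study; no telephone contact, symptom question or examination within the interval is asked for. Under Protocol 6.5 a subject is lost to follow-up only after two documented telephone attempts and a certified letter, so an unresponsive subject can remain formally enrolled for some time.

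The protocol schedules no imaging, so the physical examination is the planned means of detection, and the Note applies to subjects who did not have it. This matters most late in follow-up. Protocol 1.3.1 describes significant fibre degradation within 12 to 18 months, with loss of mechanical strength, so the 18- and 24-month examinations carry much of the information on durability. No scheduled visit follows month 24, so a recurrence missed there may never be recorded.

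Elsewhere the SAP is stricter with missing information. SAP 4.3 treats subjects who discontinue before day 45 without an SSO as not evaluable, and SAP 5.4 counts an adverse event with missing device relationship as related. SAP 5.2 makes the favourable assumption, and the sensitivity analyses in SAP 4.4 cover only the primary endpoint. SAP 6 mentions Kaplan-Meier output for some secondary endpoints, but does not name recurrence or give a censoring rule for it.

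**Working it through.** **Inputs.** About 120 treated subjects (Protocol 5.1, SAP 2.4) and exact binomial intervals (SAP 5.2). The sample size is stated not to rest on any statistical consideration, and no recurrence or missed-visit rate is given, so there is no planned figure to reproduce. Every rate below is an assumption. For simplicity, all 120 are taken to be still enrolled when the interval begins.

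**Step 1: SAP rate against examined-only rate.** Let N be the subjects in the interval, m the fraction not examined and x the recurrences recorded.

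- SAP rate = x / N
- Examined-only rate = x / [N(1 − m)]
- Ratio = 1 − m

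If x = 0 both rates are zero. Otherwise the SAP rate is the lower one.

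| Assumed case | SAP rule (95% CI) | Examined only (95% CI) |
|---|---|---|
| 20 of 120 missed, 6 events | 6/120 = 5.0% (1.9 to 10.6) | 6/100 = 6.0% (2.2 to 12.6) |
| 24 of 120 missed, 10 events | 10/120 = 8.3% (4.1 to 14.8) | 10/96 = 10.4% (5.1 to 18.3) |

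The SAP intervals are also narrower, because unexamined subjects count as observed.

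**Step 2: later detection.** Intervals follow the recurrence start date, so a later finding can repair an earlier interval if it is dated back. With true rate r in all subjects and a fraction f of the missed recurrences later found and dated back, the expected SAP rate is r[(1 − m) + mf]. For r = 10% and m = 20%:

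- f = 0: 10% × 0.80 = 8%
- f = 0.5: 10% × (0.80 + 0.10) = 9%
- f = 1: 10% × (0.80 + 0.20) = 10%, no bias

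**Step 3: unequal risk, no later detection.** Let non-attenders recur at k times the examined rate r. The truth is r[(1 − m) + mk], the SAP rule expects r(1 − m), and examined-only expects r. With r = 10% and m = 20%, the SAP rule gives 8% and examined-only 10% throughout:

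- k = 0: truth 8%. The SAP rule is right and examined-only is too high.
- k = 1: truth 10%. Examined-only is right.
- k = 2: truth 12%. Both are too low, the SAP rule more so.

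**Step 4: later negative examinations.** Under the fix below, a later negative examination restores a missed interval. If 15 of the 20 non-attenders in the first case are later examined and found clear, the rate is 6/(100 + 15) = 6/115 = 5.2%, close to the SAP's 5.0%.

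**The case against.** The rule is openly stated, and the plan has other ways of catching a recurrence. Protocol 6.3.4 sends any abdominal evaluation during follow-up to unscheduled-visit procedures, which include a physical examination (Protocol 6.4). Protocol 6.3.3 requires a recurrence seen on imaging done for any reason to be recorded. Recurrence is one of eight secondary endpoints in a study without a formal hypothesis, and the intervals in the illustration largely overlap. All of this stands and limits the weight of the point. It does not remove it: these routes work only if the subject presents for care, and the Note covers subjects with nothing recorded.

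Two stronger readings are tempting.

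- **A reader might infer that the Note breaches a protocol ban on imputation.** Protocol 7.3 does say: "The calculation of rates at each time point will be based on available data at the time point. Missing data will not be imputed". But those sentences sit in the paragraph on the primary SSO endpoint. The next paragraph, which covers recurrence, has no missing-data rule. The mention of rates at each time point can be read generally, but the protocol does not expressly apply it to recurrence. It is supporting context, not a clear contradiction.
- **A reader might infer that the rates are certainly understated, by the fraction of visits missed.** That needs equal risk in non-attenders and no later detection with back-dating. The documents establish neither, and Steps 2 to 4 show the gap shrinking or vanishing when they fail.

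**Conclusion.** The point holds in a conditional form. The Note scores subjects without an assessment as non-events on an endpoint that the protocol and SAP define by investigator finding. Relative to an examined-only analysis it can leave the interval rate unchanged or lower it, never raise it. Relative to the truth, the rate is understated and its interval too narrow whenever a non-attender has a recurrence that is not later found and dated back.

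The size cannot be derived from the documents. Under assumed equal risk and no later detection, the SAP rate is the examined-subject rate times the fraction examined, for example 5.0% in place of 6.0% with 20 of 120 unexamined. Where later examinations cover the missed visit, the effect is smaller. The change is worth making because the outcome bears on durability, the rule is untested, and the repair uses data already collected.

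**What to change.** Replace the Note in SAP 5.2 with a rule to this effect for each disjoint interval:

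1. A subject is evaluable only with (a) a recurrence whose start date falls in the interval, or (b) an examination or abdominal imaging, in the interval or later, that shows no recurrence.
2. A subject not examined in the interval whose recurrence is first recorded later is an event in the interval of the recorded start date, and is not evaluable for the missed interval.
3. A subject never examined or imaged in or after the interval, with no recorded recurrence, is not evaluable for it.

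Report the numbers examined and missed per interval, and keep the present rule as a labelled best-case sensitivity analysis. For the cumulative rates, where every implanted subject stays in the denominator, add a time-to-event estimate that censors subjects at their last recurrence assessment.

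The cost is SAP wording and derivations from visit data already collected. Denominators become slightly smaller and the rate possibly less favourable. The rule still leans a little low for a missed interval, because a later clear examination restores a subject and a later positive one dated to its own interval does not. The reported counts would show how many subjects this affects.

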### **5.3 Surgical Pain Scale - Visual Analog Scale (VAS)**

Subjects complete the pain VAS with 0 cm = “no pain” to 10 cm = “the worst pain imaginable” at baseline and at all post procedure visits.

The pain VAS length (cm) and its absolute change from baseline will be described with summary statistics by visit. Summary statistics by visit and absolute change from baseline will be presented with and without subjects taking pain medication within 24 hours of the pain VAS date. Analysis is based on mITT population.

### **5.4 Device Related Adverse Event Incidence**

Adverse events that are possibly or definitely related to device will be included in the calculation of the device-related adverse event rate. In case of a missing classification of the relationship to device a relation to the device is assumed.

The proportion of subjects with device-related adverse event rate and confidence intervals of the rate from exact binomial test will be reported by each visit window, including both cumulative (overall rate) and disjointed intervals.

The start date of the device-related adverse event rate minus the implantation date will determine the interval of device-related adverse event.

A frequency table grouped by the Medical Dictionary for Regulatory Activities (MedDRA) dictionary of terms (system organ class (SOC) and preferred term (PT)) will be presented for number of subjects with device related AEs and total number of AEs.

Frequency tables for device related AEs by visit (presenting the number of subjects with events and total number of events) will be displayed.

Analysis is based on mITT population.

### **5.5 Rate of Reoperation due to Index Hernia Repair**

The proportion of subjects with reoperation due to the index hernia repair and confidence intervals of the rate from exact binomial test will be reported by visit, including both cumulative and disjoint intervals.

Reoperation date will be compared to surgery date to determine the interval of reoperation.

Only evaluable subjects will be included in the denominator and evaluable subjects are defined as following: 1) For cumulative intervals, any subjects with Phasix™ ST Mesh implanted will be included in this analysis. 2) For disjoint intervals, if a subject discontinues before the intervals begins then that subject is considered as not evaluable for that particular interval analysis. Analysis is based on mITT population.

### **5.6 Quality of life assessments (Carolinas Comfort Scale® and SF-12v2™)**

#### **5.6.1 Carolinas Comfort Scale® (CCS)**

The CCS is a 23-item questionnaire that measures sensation of mesh, severity of pain and movement limitations in the following eight domains: laying down, bending over, sitting up, performing activities of daily living, coughing or deep breathing, walking, walking up the stairs and exercising. The CCS is completed by the subjects at baseline and at all post

procedure visits. Each scale (sensation of mesh, pain or movement limitations) score (ranges from 0-5) is the average across the domains, and the total score (ranges from 0-5) is the average of the three scales scores.

CCS will be analyzed in accordance to the CCS user guide. Computational algorithms including the handling of missing values are described in detail in the guideline. In summary, the following rules will be applied:

1. Questions outcomes 0-5 will be used with lower scores indicating a more favorable health status.
2. Not applicable or no response will be handled as missing values.
3. Two or more outcomes ticked per question will be handled as missing value.

Absolute values and changes from baseline will be summarized with mean, standard deviation, minimum, median and maximum for each scale score and total score at each post baseline visit (except drain removal).

For each subject at each visit, if less or equal to two responses are missing within any of the three scales, the missing values will be replaced by the mean of the remaining responses of the scale at that visit. If more than two responses are missing within any scale for a visit, the whole survey at that visit will not be used for that subject.

Analysis is based on mITT population.

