6.1.10 Patient Reported Outcome Assessments

Subjects will complete the Surgical Pain Scale -VAS, Carolinas Comfort Scale® and SF-12® to measure pain, discomfort and quality of life.

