6.2 Surgical Procedure

6.2.1 General Procedures

All subjects will undergo laparoscopic ventral hernia repair. Subjects will be administered pre-operative antibiotics according to hospital protocol. There is an intraoperative exclusion for hernias $>350 \text{ cm}^2$. All other intraoperative exclusion criterion should be verified (e.g., a

surgical wound classified as clean-contaminated, contaminated or dirty; absence of an active or latent systemic infection; presence of peritonitis; a hernia bridge as the sole repair procedure) as final eligibility is determined intraoperatively.

The surgical technique will require intraabdominal (using absorbable sutures or tacks) mesh placement (with or without CST). Ensure proper orientation (see IFU for details); the coated side of the prosthesis should be oriented against the bowel or sensitive organs. Do not place the uncoated mesh side against the bowel. There is a risk for adhesion formation or erosions when the uncoated mesh side is placed in direct contact with the bowel or viscera.

The Phasix™ ST Mesh can be tailored without fraying or unraveling and offers bi-directional elasticity to adapt to various stresses encountered in the body. Use a sharp surgical instrument (scissors) to trim the mesh. To minimize chance of recurrence, trim the mesh such that it is large enough to provide sufficient overlap beyond the margins of the defect. If the material is cut too small, tension may be placed on the suture line, which may result in a recurrence of the original defect. The mesh is to be positioned so its edges extend beyond the margins of the defect by at least 5 cm. It is recommended that fixation be placed at approximately every 1 to 2 cm intervals. The edges are then fixated to assure proper closure under correct tension.

If a prior hernia repair utilizing mesh is in the same area to be treated for the study, complete removal of existing mesh is required for the subject to remain eligible for the study. Subjects with intact permanent mesh adjacent to the study hernia to be repaired are excluded from the study. Once all of the dissection is performed and all of the hernia has been exposed, the largest vertical and transverse dimensions should be recorded.

The procedure may include CST to obtain site closure. All skin incisions will be closed with staples and/or sutures and wounds will be dressed with sterile occlusive dressings.

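### SAP 5.6.1 takes change from baseline for CCS mesh sensation, and for a total containing it, although no study mesh is present at baseline; these two change scores are not interpretable

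*SAP*

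**What the plan says.** The Protocol lists the CCS among the screening and baseline procedures (6.1.10): "Subjects will complete the Surgical Pain Scale -VAS, Carolinas Comfort Scale® and SF-12® to measure pain, discomfort and quality of life". The Table of Study Events repeats it at each follow-up visit. SAP 5.6.1 likewise has subjects fill in the CCS once before surgery and again at each visit after it.

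On scoring, the SAP states: "Each scale (sensation of mesh, pain or movement limitations) score (ranges from 0-5) is the average across the domains". The three scales are then combined with equal weight into a total on the same 0 to 5 range, so mesh sensation makes up one third of it. On direction: "Questions outcomes 0-5 will be used with lower scores indicating a more favorable health status".

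The planned summary is: "Absolute values and changes from baseline will be summarized with mean, standard deviation, minimum, median and maximum for each scale score and total score". The only visit set aside in that sentence is drain removal. No exception, pre-operative version or baseline scoring rule is given for mesh sensation.

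Two further rules in SAP 5.6.1 matter. A not-applicable answer counts as missing, and more than two missing answers in any one scale remove the whole survey for that visit. Scoring is otherwise referred to a CCS user guide.

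On prior mesh, the Protocol excludes subjects with four or more earlier repairs of the index hernia (5.2.2), so up to three are allowed. Where an earlier mesh lies in the area to be treated, Protocol 6.2.1 says "complete removal of existing mesh is required for the subject to remain eligible for the study".

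**The concern.** A change score needs the same thing to be measured at both times. Pain and limitation of movement exist before and after a hernia repair. Sensation of the study mesh exists only after it.

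A subject without prior mesh has nothing to rate at baseline. If the answer is 0, the scale starts at its floor and can only stay there or worsen. A subject with prior mesh rates a device that is taken out at surgery, so the change compares two meshes. The total inherits both problems with a weight of one third.

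Quality of life is a named secondary endpoint, and in a single-arm study change from baseline is the only within-study comparison for the CCS. The mean change in the total would move with the proportion of subjects who have prior mesh, even if the benefit in pain and movement were the same for everyone. No planned CCS table would show this: SAP section 6 does not list prior mesh as a subgroup, and its further subgroups are for the primary endpoint only.

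**Working it through.** The documents give no expected CCS values, so there is no planned figure to reproduce. The scoring rule is the SAP's; the scores below are assumptions chosen to show the range.

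**Formulas.** Let S, P and M be the sensation, pain and movement scores.

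- Total = (S + P + M)/3, so change in total = (ΔS + ΔP + ΔM)/3.
- Mean pain/movement change = (ΔP + ΔM)/2.
- Hence change in total = ΔS/3 + (2/3) × mean pain/movement change.

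**Bound when baseline S is 0.** ΔS equals the post-operative S and cannot be negative. When pain and movement improve, the total therefore shows at most two thirds of their mean improvement, and that only if post-operative sensation is zero.

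**When the total matches or exceeds.** The two changes are equal when ΔS equals the mean pain/movement change. The total change is larger when sensation falls by more than that.

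**Worked cases.** Pain and movement each fall from 2 to 1, so the mean pain/movement change is -1.00 in every row.

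| Sensation, baseline to follow-up | Baseline total | Follow-up total | Change in total |
|---|---|---|---|
| 0 to 0 | (0+2+2)/3 = 1.33 | (0+1+1)/3 = 0.67 | -0.67 |
| 0 to 0.5 | 1.33 | 2.5/3 = 0.83 | -0.50 |
| 0 to 1 | 1.33 | 3/3 = 1.00 | -0.33 |
| 0 to 2 | 1.33 | 4/3 = 1.33 | 0.00 |
| 1 to 0.5 | 5/3 = 1.67 | 0.83 | -0.83 |
| 2 to 1 | 6/3 = 2.00 | 1.00 | -1.00 |
| 2 to 0.5 | 2.00 | 0.83 | -1.17 |
| 2 to 0 | 2.00 | 0.67 | -1.33 |

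**Case mix.** Suppose a share q of subjects goes from 2 to 0.5 on sensation (prior mesh) and the rest from 0 to 0.5. Mean ΔS = -1.5q + 0.5(1 - q) = 0.5 - 2q, and mean change in total = (0.5 - 2q - 2)/3 = (-1.5 - 2q)/3.

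- q = 0: -0.50
- q = 25%: -0.67
- q = 50%: -0.83
- q = 75%: -1.00
- q = 100%: -1.17

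The pain and movement benefit is -1.00 throughout.

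**The not-applicable route.** The SAP describes 23 items over three scales and eight domains. Since 3 × 8 = 24, one scale has seven items; which one is not stated. A subject who marks every sensation item not applicable has 7 or 8 missing, which is more than 2, so the whole baseline survey is dropped and no CCS change can be computed, including for pain and movement. If 25%, 50% or 75% of 120 subjects answered this way (assumed shares), 90, 60 or 30 usable baselines would remain.

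**The case against.** The strongest reply is that the SAP already reports each scale separately. The pain and movement changes are there, undiluted, and post-operative mesh sensation appears as absolute values. A reader can ignore the total. The endpoint is descriptive, the study has no hypothesis, and no test or sample size depends on it. All of this stands and limits the weight of the point. It does not give meaning to the two change scores that the SAP also prescribes.

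Secondly, scoring follows a CCS user guide that was not available, and that guide may contain a baseline rule. This stands as a caveat. The SAP's own summary of the rules gives none, and its text asks for change on every scale.

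Thirdly, new mesh sensation after implantation is a real burden, and counting it in the total is not bias. This also stands. It is why the two-thirds figure describes how the total relates to pain and movement, and is not a measure of lost truth.

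A reader might go further and infer that completed surveys understate improvement in general. The documents do not support this. They allow prior mesh, for which the total can match or exceed the pain and movement change. A subject without mesh is also not bound to answer 0: the not-applicable answer exists, and nothing prevents a non-zero answer that reflects the hernia itself. If not-applicable baselines are discarded, the remaining sample could hold proportionally more subjects with prior mesh. Nor do the documents give the change in total any leading status among the CCS summaries.

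**Conclusion.** The point holds for two of the four CCS change scores: mesh sensation and the three-scale total. Neither compares the same construct before and after surgery, so neither can be interpreted as planned.

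The size depends on how baseline sensation is answered. With a score of 0, the total shows no more than two thirds of the pain and movement improvement; in the assumed cases it shows between two thirds and none of it. With prior mesh, the assumed cases run from -0.83 to -1.33 against -1.00. With not-applicable answers, the baseline survey is lost altogether. The documents do not give the share of subjects in each group, so the net direction is unknown.

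This is worth correcting because the correction is nearly free. It affects the reading of one descriptive secondary endpoint and does not touch the primary analysis. The conclusion assumes that the user guide contains no baseline rule that overrides the SAP text.

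**What to change.** In SAP 5.6.1:

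- Report change from baseline only for the pain and movement-limitation scales. If a single summary is wanted, add their two-scale average, computed in the same way at all visits.
- Report mesh sensation and the three-scale total as absolute post-operative values by visit, without change from baseline.
- Exempt the baseline mesh-sensation items from the rule that discards a survey with more than two missing answers in a scale, so that baseline pain and movement scores are kept. Without this step, subjects who mark those items not applicable would still lose their pain and movement change.

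The cost is SAP wording and table shells; no new data are needed. The two-scale average would be an addition to the plan and should be labelled as such. The small downside is that change in the three-scale total is no longer reported.

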### **2.3 Overview**

This is a prospective, multi-center, single-arm, open-label study designed to collect additional data on the safety, performance and effectiveness of Phasix™ ST for laparoscopic ventral or incisional hernia repair. Follow-up visits will be conducted at 1, 3, 6, 12, 18, and 24-months following surgery.

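### Unanswered mesh-sensation items at baseline void the whole Carolinas Comfort Scale survey, so complete pain and movement change scores are lost as well

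*SAP*

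**What the plan says.** SAP 5.6.1 describes the CCS as a 23-item questionnaire with three scales (sensation of mesh, pain, movement limitation) asked across eight activity domains. On timing, "The CCS is completed by the subjects at baseline" and again at every visit after the procedure. Protocol 6.1.10 and the schedule in Protocol 6.4 place that first completion in screening and baseline, ahead of device placement.

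On scoring of the scales: "Each scale (sensation of mesh, pain or movement limitations) score (ranges from 0-5) is the average across the domains". The overall score is then built from these three results: "the total score (ranges from 0-5) is the average of the three scales scores".

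On missing answers: "Not applicable or no response will be handled as missing values". A question with two or more boxes ticked is also missing. If a scale has one or two missing items, they are filled with the mean of that scale's remaining answers. Beyond that, "If more than two responses are missing within any scale for a visit, the whole survey at that visit will not be used".

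On output: "Absolute values and changes from baseline will be summarized with mean, standard deviation, minimum, median and maximum for each scale score and total score".

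The SAP says it follows the CCS user guide: "Computational algorithms including the handling of missing values are described in detail in the guideline". Neither document exempts the mesh items at baseline, scores them as zero before implantation, or provides a scale-by-scale fallback.

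**The concern.** Eligibility requires a ventral or incisional hernia, not an earlier mesh repair. A subject with no mesh in place has nothing to report on the mesh-sensation items, and not applicable is then a truthful answer. The SAP foresees that answer but treats it as missing, and enough such answers in one scale cancel the other two.

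The scoring does not need this. Each scale is averaged on its own, and only the total depends on all three.

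Two things are at stake. First, valid pain and movement answers could be discarded because of items that the subject could not meaningfully answer. Second, the loss could be selective. Protocol 5.2.2 allows up to three earlier repairs of the index hernia, and Protocol 6.2.1 requires existing mesh in the same area to be removed at the study operation. Some subjects may therefore have mesh in place when they fill in the baseline form and be able to answer it. The change scores could then over-represent subjects with prior mesh.

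**Working it through.** **Inputs**
- Rules on missing items, scale averages and the total: SAP 5.6.1.
- Timing of baseline before implantation: Protocol 6.1.10 and 6.4.
- Six follow-up visits: "Follow-up visits will be conducted at 1, 3, 6, 12, 18, and 24-months following surgery" (SAP 2.3).
- About 120 treated subjects: SAP 2.4. The SAP says this number has no statistical basis, so there is no planned precision to reproduce.
- Assumed layout: 8 mesh + 8 pain + 7 movement = 23 items. Three scales by eight domains would give 24, one more than the stated 23. The result does not depend on which scale has seven.

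**Step 1. Apply the rule as written.** Let *m* be the number of mesh items missing at baseline, with pain and movement fully answered. Invented values for illustration: at baseline, answered mesh items 0, pain items 3, movement items 2; at follow-up, every item 1.

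| *m* | Baseline survey | Change in mesh / pain / movement / total | Answered items discarded (23 − *m*) |
|---|---|---|---|
| 0, 1 or 2 | kept | +1 / −2 / −1 / −0.67 | 0 |
| 3 | void | none available | 20 |
| 8 | void | none available | 15 |

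The outcome switches between *m* = 2 and *m* = 3, and every value from 3 to 8 gives a void baseline. The follow-up absolute scores are the same in every row.

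**Step 2. Count the change scores per subject.**
- Planned: (3 scales + 1 total) × 6 visits = 24.
- Current rule, baseline void: 24 lost, 0 kept.
- Voiding within the scale: mesh 6 + total 6 = 12 lost; pain 6 + movement 6 = 12 kept.

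The loss due to survey-level voiding alone is therefore 12 pain and movement change scores per affected subject, given otherwise complete surveys.

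**Step 3. Effect on N.** With *k* affected subjects out of 120, N for a pain or movement change score is at most 120 − *k* under the current rule and at most 120 under the within-scale rule. The documents do not give *k*. The fractions below are assumptions that show the range. The half-width of a 95% confidence interval for a mean change, in SD units, is 1.96/√N.

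| Assumed share affected | N left | Half-width (SD) |
|---|---|---|
| 0% | 120 | 0.18 |
| 10% | 108 | 0.19 |
| 25% | 90 | 0.21 |
| 50% | 60 | 0.25 |
| 75% | 30 | 0.36 |
| 90% | 12 | 0.57 |

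The loss of precision is modest unless a large share is affected. The table says nothing about bias from selective loss, which the documents give no means to quantify.

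**The case against.** The strongest reply is that the SAP defers to a user guide that is not in the documents. If the guide covers completion before implantation, for instance by omitting the mesh items or scoring them as zero, the problem may not arise. That possibility stands. However, the voiding rule is written into the SAP as an instruction for every subject at every visit, with no baseline exception. A programmer working from the SAP would void the survey. If the guide has a provision, the SAP should state it.

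The trigger is also unproven. Answers run from 0 to 5 with lower being better, so a subject without mesh may enter 0 throughout and the survey is kept. The documents give no baseline completion instruction or completion rate. This stands: *k* may be zero.

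Half of the 24 lost scores would be lost under the proposed fix too. That is correct, and the count above separates them.

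The selectivity argument has no figure behind it. The Protocol does not say how many earlier repairs used mesh, and it excludes subjects with intact permanent mesh adjacent to the hernia or with mesh that cannot be fully removed. It remains a possibility only.

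Within-scale voiding at all visits goes further than the baseline problem requires and may depart from the guide. This is fair, and a baseline-only version would meet it.

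Finally, the impact is small. SAP 4.2 states no hypothesis, and the CCS is part of one of eight secondary endpoints (SAP 2.2.2). Change in pain VAS (SAP 5.3) and the SF-12v2 (SAP 5.6.2) cover related ground. This stands and sets the severity.

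**Conclusion.** The point holds and is minor. As written, three or more mesh-sensation items left unanswered or marked not applicable at baseline discard that subject's complete pain and movement baseline and all 24 planned CCS change scores. Twelve of those could be kept. Post-operative absolute CCS values are untouched by the baseline problem, and so is the primary endpoint.

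The conclusion assumes that the SAP text is applied literally and that the user guide contains no overriding pre-implant provision. The total effect depends on *k*, which is unknown. Confidence is medium for these reasons.

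**What to change.** - **Preferred change to SAP 5.6.1:** for scale scores and their changes from baseline, apply the more-than-two-missing rule within each scale, so that only the affected scale and the total are void at that visit.
- **Minimum change:** state that mesh-sensation items missing or marked not applicable at baseline do not void the baseline pain and movement scores.
- **In either case:** keep mesh-sensation change from baseline for subjects with a valid baseline mesh score, and report the N behind each change score.
- **User guide:** check it for a pre-implant provision and write that provision into the SAP. If the guide requires survey-level voiding, declare the departure or show the guide-scored result alongside.

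The cost is a few lines of SAP text and a small change to the scoring program, with no new data. The downside is slightly less comparability with studies that use the guide's rule, or one extra table if both versions are shown. Settling it in advance avoids a scoring decision made after the data have been seen.
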